6.3 Management of nausea and vomiting for trials investigating monotherapy of Nintedanib

In order to reduce the occurrence and the intensity of emesis the patients should be treated according to the following recommendations:

CTCAE v4.0 Grade	Antiemetic treatment	Dose of Nintedanib
Nausea =1	No antiemetic treatment	No dose reduction
Nausea 2 and/or vomiting =1	No Nintedanib treatment pause Antiemetic treatment according to local standard of care, e.g., metoclopramide or dimenhydrinate, or prochlorperazine If ineffective, patients should be treated according to treatment of vomiting ≥ 2 or nausea CTCAE Grade ≥ 3 .	No dose reduction
Vomiting ≥ 2 and/ or nausea ≥ 3		
First episode	Treatment with Nintedanib discontinued and resumed upon recovery ¹ Antiemetic treatment according to local standard of care e.g., with 5-HT ₃ receptor antagonist* and/or corticosteroid	Nintedanib: dose reduction ²
Second episode	Treatment with Nintedanib discontinued and resumed upon recovery ¹ Treatment as above	Nintedanib: dose reduction ²
Third episode	As above	Nintedanib: discontinuation

¹CTCAE grade ≤ 1 or baseline at study enrolment.

²Nintedanib dose reductions : from 200 mg bid to 150 mg bid and from 150 mg bid to 100 mg bid

* Note: Tropisetron and dolasetron should be avoided due to genetically polymorphic metabolism by CYP2D6.

THIS SPACE LEFT INTENTIONALLY BLANK

6.4 Management of non-hematologic adverse events other than emesis, liver enzyme elevations, and diarrhea

CTCAE v4.0 Grade 3 or 4	Nintedanib
First Episode	TEMPORARILY Stop Nintedanib treatment until recovery ¹ Then Nintedanib dose reduction ²
Second Episode	TEMPORARILY Stop Nintedanib treatment until recovery ¹ Then Nintedanib dose reduction ²
Third Episode	PERMANENT Nintedanib treatment discontinuation

¹Until resolution to less than or equal to the patient's pre-therapy value at study enrollment.

²Nintedanib dose reductions : from 200 mg bid to 150 mg bid and from 150 mg bid to 100 mg bid

6.5 Patients should PERMANENTLY discontinue treatment with Nintedanib in the event of:

- Intolerable Adverse Events (CTCAE v4.0 grade 3 or 4) that cannot be managed by dose reduction.
- Nausea or vomiting CTCAE v4.0 grade 2 for 5 or more consecutive days despite optimal supportive care and dose reduction of study medication.
- Diarrhea CTCAE v4.0 grade ≥ 2 for 8 or more consecutive days despite optimal supportive care and dose reduction of study medication.
- In the event that Nintedanib is withheld for > 21 consecutive days due to treatment-related toxicity, Nintedanib will be permanently discontinued.

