5.3 Criteria for removal from treatment

5.3.1 Inability to tolerate Nintedanib at the lowest doses because of toxicity.

5.3.2 Patients may choose to withdraw from the study at any time for any reason.

5.3.3 Patients with evidence of disease progression or significant side effects will be removed from study.

5.3.4 Patients who become pregnant will be removed from the study.

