10.4 Adverse Events and Laboratory Values of Special Interest

Adverse events of special interest are to be reported using the same time line as Serious Adverse Events, even if they do not meet any of the seriousness criteria:

1. **Any gastrointestinal and non-gastrointestinal perforation, leakage, fistula formation, and abscess.** In such case, the following additional information need to be collected, documented on the eCRF page and forwarded to Boehringer Ingelheim:
 - Location/extent of abdominal tumor magnifications.
 - Imaging and reports (CT, ultrasound, endoscopy, pathology, etc.).
 - Prior surgery (location, wound healing complications).
 - Concomitant diseases with GI involvement (e. g. Crohn's, vasculitis, tuberculosis, diverticulitis).
2. **Elevated transaminases:** based on laboratory values.
 - (i) ALT and/or AST $> 5x$ ULN without bilirubin elevation.
 - (ii) ALT and/or AST $> 3x$ ULN with bilirubin $> 1.5x$ ULN.
 - (iii) Occurrence of at least two (2) elevated results no more than 2 weeks apart that is not considered to be an adverse event.

In such case, the following additional information needs to be collected, documented as an adverse event or medical history if applicable, and included on the Boehringer Ingelheim SAE reporting form:

- Hepatic tumor involvement.
- Gilbert syndrome.
- Viral hepatitis (e.g., Hepatitis A; B; C; EBV; CMV).
- Alcohol and/or autoimmune hepatitis.
- Hepatobiliary disorders (e.g., gallstones).
- Vascular hepatitis conditions (e.g., portal vein thrombosis, right heart failure).
- Recent alcohol consumption.
- Recent intake of hepatotoxic compounds (including steroids).
- Other etiology.

Medical evaluation of these results and clinical documentation should be provided.

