10.10 Recording Adverse Events

Classification of Adverse Events

****AEs that do not meet any of the criteria for serious should be regarded as non-serious AEs.** The terms “severe” and “serious” are not synonymous.

Severity (or intensity) refers to the grade of a specific adverse event (e.g., mild; moderate; or severe).

Ex. A **severe** rash is not likely to be an **SAE**. Likewise, a **severe** headache is not necessarily an **SAE**. However, **mild** chest pain may result in a day’s hospitalization and thus is an **SAE**.

“Serious” is a regulatory definition (see above) and is based on subject or event outcome or action criteria usually associated with events that pose a threat to a subject’s life or functioning. Seriousness (not severity) serves as the guide for defining regulatory reporting obligations from the Sponsor to applicable regulatory authorities. Severity and seriousness should be independently assessed when recording AEs and SAEs on the CRF.

Collection of complete information concerning SAEs is extremely important. Full descriptions of each event will be followed. Thus, follow-up information which becomes available as the SAE evolves, as well as supporting documentation (e.g., hospital discharge summaries and autopsy reports), should be collected subsequently, if not available at the time of the initial report, and immediately sent using the same procedure as the initial SAE report.

The investigator must categorize the severity of each adverse event according to the following guidelines:

Criteria:

NCI toxicity criteria will be followed. Special attention will be paid to gastrointestinal, non-gastrointestinal perforation, leakage, fistula formation, abscess, and elevated transaminases.

Mild:	Grade I NCI Common Toxicity
Moderate:	Grade II NCI Common Toxicity
Moderately:	Severe: Grade III Common Toxicity
Severe:	Grade IV NCI Common Toxicity
Death:	Grade V NCI Common Toxicity

If the event is not found in the NCI Common Toxicity table, the adverse event will be scored using 5 grades:

Grade 1	Causing no limitation of usual activities
Grade 2	Causing some limitation of usual activities
Grade 3	Causing some inability to carry out usual activities
Grade 4	Causing life-threatening or disabling toxicity
Grade 5	Causing death

NCI Common Toxicity for Adverse Event Grading (Severity) Chart v4.0

Grade	Severity (Intensity)	Alternative Description

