Information for final description and evaluation of a case report may not be available with the required time frames for reporting. Nevertheless, for regulatory

purposes, initial report shall be submitted within the prescribed time as long as the following minimal requirements are met:

The ***initial*** report for each SAE should include at minimum the following information:

- Protocol # and title.
- Regulatory Seriousness criteria if applicable (i.e., death; life-threatening; hospitalization; etc.).
- Patient initials, study identification number, sex, and age.
- Date the event occurred (onset).
- Severity (intensity) - see chart.
- Description of the SAE.
- Dose level and cycle number at the time the SAE occurred.
- Description of the patient's condition.
- Indication whether the patient remains on study.
- Causality (relationship of the event to the study medication).

Follow-up information may include:

- Severity (intensity) - see chart.
- Duration of the event.
- Treatment and/or medication(s) given for the event, if any.
- Brief narrative summarizing the relevant details of the event.
- Action taken to study medication.
- Concomitant medications.
- Event outcome with dates should be communicated to the Duke as soon as possible.
- When applicable and requested, information from relevant hospital records (e.g., discharge summary, autopsy reports, etc.).

Upon receipt of the Serious Adverse Event Report Form by Duke, DCI Safety will:

- a. Notify [name] of the event via email and obtain an assessment for each event via the SAE Review Form.
- b. Fax the form to Boehringer Ingelheim Global Pharmacovigilance Center US (GPV Centre US) at [name]

All adverse events, regardless of severity, and whether or not ascribed to the study drug administration, will be recorded in the appropriate section of the Case Report Form. Patients withdrawn from the study due to AEs will be followed by the Investigator until the outcome is determined and, when appropriate, additional written reports and documentation will be provided.

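### Section 6.4 permits a dose-reduced restart after a resolved grade 3-4 perforation, fistula, stroke or MI, with no event-specific stop and no stated order of precedence

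*Combined protocol and SAP*

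**What the plan says.** Section 6.4 is the residual dosing rule for grade 3-4 non-hematologic events. Diarrhea (6.1), liver enzymes (6.2) and nausea and vomiting (6.3) have their own tables; everything else falls here. For a first and for a second episode it says "TEMPORARILY Stop Nintedanib treatment until recovery", then lowers the dose by one level. Recovery means a return to the pre-therapy value or better. The third episode is a permanent stop.

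Section 6.5 lists the permanent stops. Two are general: "Intolerable Adverse Events (CTCAE v4.0 grade 3 or 4) that cannot be managed by dose reduction", and a dose "withheld for > 21 consecutive days due to treatment-related toxicity". The other two concern prolonged nausea or vomiting and prolonged diarrhea.

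Section 5.3 lists criteria for removal. Item 5.3.1 is "Inability to tolerate Nintedanib at the lowest doses because of toxicity". Item 5.3.3 is "Patients with evidence of disease progression or significant side effects will be removed from study".

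Section 10.4 puts two groups of events on the SAE reporting timeline whether or not they are serious. One is "Any gastrointestinal and non-gastrointestinal perforation, leakage, fistula formation, and abscess"; the other is elevated transaminases. Section 10.10 repeats the emphasis: "Special attention will be paid to gastrointestinal, non-gastrointestinal perforation, leakage, fistula formation, abscess, and elevated transaminases". On receipt of an SAE form, the coordinating center's safety desk is to notify the sponsor-investigator and "obtain an assessment for each event via the SAE Review Form" (10.11).

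**The concern.** Nintedanib is an anti-angiogenic drug, and the protocol itself treats perforation and fistula as events of special interest. The dosing rules do not follow through. Of the two special-interest groups, transaminases have a dosing algorithm of their own in 6.2, while perforation, leakage, fistula and abscess have only a reporting duty and so fall into the general restart path. Stroke and MI are not on the special-interest list and fall into the same path.

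What is at stake is patient safety and consistency between sites. In this multi-center trial, a site that follows 6.4 may restart the drug in a patient who has recovered from a perforation or an MI, and a site that follows 5.3.3 removes the same patient. Both can point to protocol text.

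**Working it through.** The point turns on the wording, so no arithmetic applies beyond counting dose levels. The check takes a patient with a first grade 3 or 4 perforation, stroke or MI that resolves, and asks of each provision whether it prevents a restart.

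| Provision | Effect | Does it prevent a restart after a resolved event? |
|---|---|---|
| 6.4, restart rule | Hold, recover, restart one level lower; permanent stop at the third episode | No. It directs the restart, whatever the attribution |
| 6.4, recovery condition | Requires return to the pre-therapy value | Only if a deficit persists |
| 6.5, first bullet | Stops intolerable grade 3-4 events that dose reduction cannot manage | Depends on judgment; an event that has resolved need not meet it |
| 6.5, 21-day rule | Stops after a hold of more than 21 consecutive days | Only for a long hold and treatment-related toxicity |
| 5.2.1 and 9.0 | Treat until progression or toxicity (intolerable toxicity in 9.0) | General; no event named, no precedence stated |
| 5.3.1 | Removes patients who cannot tolerate the lowest doses | No. It fits stepwise reduction first |
| 5.3.3 | Removes patients with significant side effects | Points to removal, but the term is undefined and not ranked against section 6 |
| 10.4 | Expedited reporting and extra data for perforation, leakage, fistula and abscess | No dosing action; stroke and MI not listed |
| 10.11 | Central assessment of each SAE | Not stated to decide dosing or to come before a restart |

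**Number of restarts.** The dose levels in section 6.0 are 200, 150 and 100 mg twice daily. Two reductions are available, so 6.4 allows at most two restarts before it requires a stop.

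**Attribution.** The 21-day rule depends on a relatedness call, and such calls vary. In the pooled monotherapy data of 4.1.9.4, two TIAs are listed and one was considered treatment-related. A hold for an event judged unrelated has no time limit under 6.5.

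**Comparison within the protocol.**
- *Entry.* Section 3.2 excludes a history of GI perforation or of abdominal or tracheal-esophageal fistula, with no time limit. It also excludes MI within six months of registration, and CVA, TIA or subarachnoid hemorrhage within six months of first treatment. An event that bars entry does not clearly bar a restart.
- *Liver.* Section 6.2 stops the drug permanently at a second episode of ALT or AST above 5 times ULN. Section 6.4 allows another restart after a second grade 3-4 perforation.
- *Emesis.* Section 6.5 names a permanent stop for grade 2 nausea or vomiting lasting five or more days despite supportive care and dose reduction. It names none for perforation, stroke or MI.

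**The case against.** The strongest reply is that 6.4 should not be read alone. Section 6.5 follows the dosing tables, and its bullets on diarrhea and on nausea and vomiting cut across them, so a sensible reader would let it override 6.4. A perforation, stroke or MI is a natural candidate for its first bullet. Lasting damage blocks restart through the recovery condition. Section 3.1 requires more than 28 days between major surgery and first dosing. A site that applied the same interval after surgical repair of a treatment-related perforation would already have passed the 21-day limit. The sponsor-investigator also assesses every SAE and monitors risk and benefit continuously (10.13). Finally, the Investigator Brochure goes to every site and cannot be seen here.

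Much of this stands. A reader might infer that 6.5 offers no stop at all, or that 5.3.3 is the only text in favor of stopping. Neither is right: the first bullet of 6.5, the 21-day rule, 5.2.1 and 9.0 all support stopping too. What is missing is an event-specific stop and a statement of which rule governs. That 6.5 overrides 6.4 is a reasonable inference, but it is not written. The 28-day interval is an entry rule, not a restart rule. The route to rechallenge is therefore narrow but open.

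It also stands that no document here requires a permanent stop for these events. Which events belong on the list is a clinical decision to be checked against the Brochure.

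**Conclusion.** The concern holds in this form: rechallenge after a resolved grade 3-4 perforation, fistula, stroke or MI is permitted by the text of 6.4, and the general provisions do not reliably prevent it. The change should be made because the consequence for a single patient could be grave and the edit is small.

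The frequency cannot be estimated. The documents give no perforation or fistula rate, and the MI and TIA counts in 4.1.9.4 carry no grade and come from trials that include higher doses, so they do not measure restarts under 6.4. A reader might also infer that the efficacy result is compromised. The documents do not support that, and no effect on six-month PFS is claimed.

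The conclusion assumes that sites follow the protocol as written, and that neither the Brochure nor the removed consent pages contain a binding dosing rule for these events.

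**What to change.** 1. Add to 6.5 a permanent-discontinuation bullet for grade 3-4 GI or non-GI perforation, leakage or fistula, and for grade 3-4 CVA, subarachnoid hemorrhage or myocardial infarction. The sponsor should decide, and state, whether lower-grade events, TIA and abscess are included, after checking the Investigator Brochure. Limiting the default list to grade 3-4 matches the scope of 6.4.
2. Add to 6.4 a sentence saying that 6.5 takes precedence and that the restart path does not apply to events listed there.
3. Optionally, cross-reference 6.5 in 5.3.3 so that its undefined term has a stated meaning.

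The cost is one bullet, one sentence and at most one cross-reference, with no added visits or procedures. The downside is that a few patients stop earlier than 6.4 now directs, including some who might have tolerated a lower dose.

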6.6 Dose escalations

There will be no dose escalations or re-escalations on this study.

THIS SPACE LEFT INTENTIONALLY BLANK

7.0 STUDY PARAMETERS

7.1 The following observations and tests are to be performed and recorded on the appropriate form(s). **Specimen requirements for translational research are provided in Section 7.3.**

Parameter	Pre-Therapy	Weekly	Prior to Each cycle	Every Other Cycle	Post Treatment Follow-up
History & Physical	X ¹		X		X
Performance Status	X ¹				
Clinical tumor measurement	X ¹		X ²		
Toxicity Assessment	X ³	X ⁷	X		
CBC/Differential/Platelets	X ³		X ⁴		X ¹⁰
Electrolytes, BUN, creatinine, Ca, Mg, PO ₄ , Urinalysis	X ³		X ⁴		X ¹⁰
Bilirubin, SGOT, SGPT, Alkaline Phosphatase	X ³		X ⁴		X ¹⁰
INR/PT/PTT ¹²	X ¹			X ¹²	
Serum Pregnancy Test (for patients of childbearing potential)	X ⁹				
Chest imaging (X-ray or CT scan of the chest)	X ¹			X ⁵	
Radiographic tumor measurement (RECIST)	X ^{1, 6}			X ⁶	X ⁶
Electrocardiogram (ECG)	X ¹			X ¹³	
CA-125	X ³		X ⁴		X
Capsule Diary			X ⁸		
Research samples	X ¹¹			X ¹¹	X ¹¹
Subject Preferences Tasks	X ¹⁴				
NFOSI-18	X ¹⁴				
FACT-GOG-Ntx	X ¹⁴				

Notes:

1. Must be obtained within 28 days prior to initiating protocol therapy.
2. For those patients whose disease can be evaluated by physical examination (i.e. nodes, pelvic mass).

3. Must be obtained within 14 days prior to initiating protocol therapy.
4. CBC/Differential/Platelets, liver function tests, creatinine, CA-125, and urinalysis must be obtained within 4 days before initiating the next cycle of treatment with protocol therapy.
5. Repeat chest imaging if initially abnormal or if required, to monitor tumor response.
6. CT scan or MRI if used to follow lesion for measurable disease every other cycle for the first 6 months; then every 3 months thereafter; and at any other time if clinically indicated based on symptoms or physical signs suggestive of progressive disease or rising serum tumor marker levels.
7. Nurse at site is to make weekly phone call to the patient during the **first two** cycles of treatment to inquire about any toxicity. The phone contact should be documented in the study participant's chart.
8. See Appendix II
9. If the patient is of child-bearing potential the serum pregnancy test must be obtained within 7 days prior to initiating protocol therapy.
10. These tests are to be done as needed at the discretion of the study doctor.
11. See section 7.3 for specimen requirements. Collect whole blood, serum, plasma, and urine pre-cycle #1, every other cycle (i.e. Cycle 3, 5, etc.), at the time of progression, and one month after study treatment is discontinued.
12. Repeat every other cycle and more frequently as clinically indicated. For patients with hepatic injury or elevated liver function tests repeat the INR/PT/PTT every cycle until the liver function tests return to baseline; then resume INR/PT/PTT every other cycle.
13. Repeat every other cycle and more frequently as clinically indicated.
14. Only for subjects enrolled at Duke

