3.0 PATIENT ELIGIBILITY AND EXCLUSIONS

3.1 Eligibility Criteria

- a) Patients must have recurrent or persistent epithelial ovarian, fallopian tube, or primary peritoneal carcinoma. Histologic documentation of the original primary tumor is required via the pathology report. The following histologic epithelial cell types are eligible:
 - o serous, endometrioid, mucinous, or clear cell adenocarcinoma;
 - o undifferentiated, mixed epithelial or transitional cell carcinoma;
 - o Brenner's Tumor;
 - o adenocarcinoma N.O.S.
- b) Patients must be considered bevacizumab-resistant, i.e., have a treatment-free interval following a response to bevacizumab (CR, PR, or SD) of less than **6 months**, or have progressed during treatment with a bevacizumab-containing therapy.
- c) Patients must have measurable disease or detectable (non-measurable) disease:
 - o Measurable disease is defined as at least one lesion that can be accurately measured in at least one dimension (longest diameter to be recorded). Each lesion must be ≥ 10 mm when measured by CT, MRI, or caliper measurement by clinical exam; or ≥ 20 mm when measured by chest x-ray. Lymph nodes must be > 15 mm in short axis when measured by CT or MRI. Tumors within a previously irradiated field will be designated as "non-target" lesions unless progression is documented or a biopsy is obtained to confirm persistence at least 90 days following completion of radiation therapy.
 - o Detectable disease in a patient is defined as one who does not have measurable disease but has at least one of the following conditions in the setting of a CA125 $>2x$ ULN:
 - Ascites and/or pleural effusion attributed to tumor
 - Solid and/or cystic abnormalities on radiographic imaging that do not meet RECIST 1.1 definitions for target lesions
- d) For patients with measurable disease, patient must have at least one "target lesion" to be used to assess response on this protocol as defined by RECIST 1.1. Tumors within a previously irradiated field will be designated as "non-target" lesions unless progression is documented or a biopsy is obtained to confirm persistence at least 90 days following completion of radiation therapy.
- e) Patients who must have a ECOG Performance Status of 0 or 1.
- f) Patients should be free of active infection requiring antibiotics (with the exception of uncomplicated UTI).
- g) Recovery from effects of recent surgery, radiotherapy, or chemotherapy

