8.1.3.4 Evaluation of Best Overall (unconfirmed) Response

The best overall response is the best time point response recorded from the start of the treatment until disease progression/recurrence (taking as reference for progressive disease the smallest sum recorded since baseline). The patient's best response assignment will depend on the achievement of both measurement and confirmation criteria in some circumstances.

Time Point Response for Patients with Measurable Disease at baseline (i.e., Target Disease)

Target Lesions	Non-Target Lesions	Biomarker CA-125	New Lesions*	Time Point Response
CR	CR	Within normal limits	No	CR
CR	Non-CR/Non-PD	Any value	No	PR
CR	NE	Any value	No	PR
PR	Non-PD or NE	Any value	No	PR
SD	Non-PD or NE	Any value	No	SD
NE	Non-PD	Any value	No	NE
PD	Any	Any value	Yes or No	PD
Any	PD**	Any value	Yes or No	PD
Any	Any	Any value	Yes	PD

*See RECIST 1.1 manuscript for further details on what is evidence of a new lesion

** In exceptional circumstances, unequivocal progression in non-target lesions may be accepted as disease progression.

CR = complete response, PR = partial response, SD = stable disease, PD = progressive disease, and NE = inevaluable.

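### Note 6 to the study calendar ties scheduled CT/MRI to measurable disease, so detectable-only patients, who count in 6-month PFS, may have no scheduled abdominal or pelvic imaging after baseline

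*Combined protocol and SAP*

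**What the plan says.** Eligibility criterion 3.1(c) states: "Patients must have measurable disease or detectable (non-measurable) disease". The second category is defined thus: "Detectable disease in a patient is defined as one who does not have measurable disease but has at least one of the following conditions". The conditions are ascites or pleural effusion attributed to tumor, or imaging abnormalities that fall short of RECIST 1.1 target lesions, in either case with CA-125 above twice the upper limit of normal.

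In the section 7.1 calendar, the row for radiographic tumor measurement is marked at pre-therapy, every other cycle and post-treatment follow-up. All three marks carry note 6, which sets the timing: "CT scan or MRI if used to follow lesion for measurable disease every other cycle for the first 6 months", then every 3 months, and "at any other time if clinically indicated based on symptoms or physical signs suggestive of progressive disease or rising serum tumor marker levels".

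Other calendar items bear on how progression might be noticed:
- History and physical are due before each cycle.
- Clinical tumor measurement is also due before each cycle (note 2): "For those patients whose disease can be evaluated by physical examination".
- Chest imaging (note 5): "Repeat chest imaging if initially abnormal or if required, to monitor tumor response".
- CA-125 (note 4): "CBC/Differential/Platelets, liver function tests, creatinine, CA-125, and urinalysis must be obtained within 4 days before initiating the next cycle of treatment".

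Section 8.1.3.2 defines progression for non-target disease as new lesions or unequivocal progression of existing ones. The time-point table in 8.1.3.4 is headed "Time Point Response for Patients with Measurable Disease at baseline". Sections 11.2.1 and 11.3 do not restrict the primary endpoint to patients with measurable disease.

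**The concern.** The decision rests on one landmark, the number of patients alive and progression-free at 6 months. A patient whose progression has occurred but has not been looked for by then is scored as a success. If one part of the population is scanned every 8 weeks and another part only when something prompts it, the second part will tend to have progression recorded later.

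The shift can go only towards declaring the drug effective. The trial has a single arm and a fixed 13% reference rate, so no control group shares the error. The Kaplan-Meier fallback in section 11.3 does not remove it, because a progression found late is dated late.

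**Working it through.** **1. Does anything else schedule the imaging?** Section 8.1.1 asks for non-target lesions to be noted throughout follow-up, without timing. Section 8.1.2 requires the same method at baseline and follow-up, again without timing. Section 8.1.3.2 says what progression is, not when to look for it. Section 8.1.4 gives a CA-125 response rule, but no CA-125 rise is defined as progression or as a numeric trigger for a scan. Note 6 is therefore the only rule that times abdominal or pelvic imaging.

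**2. The design as stated.** Inputs from section 11.3: null rate p0 = 0.13, alternative 0.27; 27 patients in stage 1, stop if 3 or fewer are progression-free; 56 in total, success if 11 or more. With X1 ~ Bin(27, p) and X2 ~ Bin(29, p):

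P(success) = sum over x = 4 to 27 of P(X1 = x) × P(X2 ≥ 11 − x)

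- p = 0.13: 0.0961 (plan: 0.10)
- p = 0.27: 0.9013 (plan: 0.90)
- P(X1 ≤ 3): 0.527 and 0.042 (plan: 0.54 and 0.04)

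The error rates reproduce. The early-termination probability under the null differs by 0.013, which does not affect this point.

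**3. Effect of missed progressions.** Let f be the share of patients with detectable-only disease and m the share of their progressions by 6 months that are not recorded by then. Neither is in the documents; both are assumptions. Assume also that the true rate is 13% in both groups and that unscanned patients remain evaluable. Then

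apparent rate = 0.13 + f × m × 0.87

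and the expected number of false successes among 56 is 56 × f × m × 0.87.

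| f | m | Apparent rate | False successes in 56 | Type I error |
|---|---|---|---|---|
| any | 0 | 0.130 | 0 | 0.096 |
| 5% | 5% | 0.13 + 0.0022 = 0.132 | 0.1 | 0.105 |
| 10% | 10% | 0.13 + 0.0087 = 0.139 | 0.5 | 0.135 |
| 20% | 20% | 0.13 + 0.0348 = 0.165 | 1.9 | 0.292 |

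**4. The same question as a delay.** Assume exponential PFS with 13% at 6 months: hazard = −ln(0.13)/6 = 0.340 per month. If detection in detectable-only patients lags by d months, their apparent 6-month rate is exp(−0.340 × (6 − d)), and the overall rate is (1 − f) × 0.13 + f × that value.

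- d = 1 month (about one CA-125 interval), group rate 0.183: type I error 0.118 at f = 10%, 0.144 at f = 20%.
- d = 2 months (about one scan interval), group rate 0.257: 0.155 at f = 10%, 0.228 at f = 20%.

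**The case against.** The best counter-argument is that note 6 was never meant to exempt anyone. It is attached to the pre-therapy mark too. If it limited the row to measurable disease, detectable-only patients would have no required baseline CT/MRI, although imaging is one of their two routes to eligibility and measurable disease has to be ruled out in all of them. The row's mark is otherwise unrestricted, and the same-method rule in 8.1.2 points the same way. This makes scanning everyone a plausible reading. It does not make it the only one, and in a multi-center study the assessment schedule behind the primary endpoint should not have two.

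The second counter-argument concerns the delay. A reader might infer that progression in these patients would surface only through symptoms or CA-125. The documents do not support that. Note 6 also names physical signs; examination is scheduled before each cycle, with clinical measurement where disease can be examined; note 5 repeats chest imaging if it was initially abnormal, which covers some patients with effusion; and death is itself a PFS event. All detectable-only patients enter with raised CA-125, which is repeated before each 28-day cycle, twice as often as the 8-week scan. These facts lower m, possibly to a small value. They do not bring it to zero, because the response to a rise or a sign is left to site judgement.

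Third, section 11.3 bases the stage 1 critical value on patients evaluable for 6-month PFS without defining the term, so an unscanned patient might be set aside and not counted as a success. That is possible, but unstated.

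**Conclusion.** The point holds as an ambiguity in the assessment schedule with a possible one-sided effect. Read literally, note 6 leaves detectable-only patients without scheduled abdominal or pelvic imaging after baseline, and no other section supplies it. On that reading 6-month PFS could be biased upward.

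Two stronger conclusions are tempting and should not be drawn. One is that the endpoint is biased: that depends on how sites read the note, which the documents do not settle. The other is that the type I error is 0.18 or 0.29: such figures need f and m values that the plan does not give (0.18 corresponds, for example, to f = 10% and m = 20%), and at f = m = 5% the change is only from 0.096 to 0.105. What the calculation does show is that the rule has little slack. About half a false success among 56 patients is enough to take the error to 0.135.

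The absence of a time-point table for non-target-only disease is missing detail and not a source of bias, since 8.1.3.2 already defines progression for these patients.

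**What to change.** Reconcile note 6 with the calendar row and with eligibility criterion 3.1(c). Reword it so that the imaging schedule already in the note applies to all patients, whether their disease is measurable or detectable-only, and state that progression in the detectable-only group is judged by the non-target criteria in 8.1.3.2. A time-point table for that group would be a convenience but is not needed to protect the endpoint.

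The sample size, stopping rule and visit schedule stay as they are. With the same imaging schedule for everyone, m in this comparison is zero and the design keeps its computed error rates of 0.096 and 0.90. The cost is the footnote wording and, at sites that read the note literally, some additional scheduled scans for the detectable-only patients. Where sites already scan everyone, practice does not change.
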